Unable to Evaluate (iUE):	Any lesion present at baseline which was not assessed or was unable to be evaluated leading to an inability to determine the status of that particular tumor for that time point.
Not Applicable (NA)	No target lesions were identified at baseline
Not Done (ND)	Radiographic imaging was not performed at this time point to evaluate the response of measurable lesions

irRECIST = immune-related Response Evaluation Criteria in Solid Tumors

* Tumor Burden = sum of diameter of target lesions

Diameters used:

For nodal disease, shortest axis

For non-nodal disease, longest diameters

Table 13. Imaging and Treatment After First Radiologic Evidence of PD per irRECIST

	Clinically Stable		Clinically Unstable/Rapid Clinical Deterioration	
	Imaging	Treatment	Imaging	Treatment
1st radiologic evidence of iPD (progressive disease by irRECIST)	Repeat imaging at ≥ 4 weeks at site to confirm iPD	May continue study treatment at the local site Investigator's discretion while awaiting confirmatory tumor imaging by site by irRECIST.	Repeat imaging at ≥ 4 weeks to confirm iPD per investigator discretion*	Discontinue treatment
Repeat tumor imaging confirms iPD (progressive disease by irRECIST) at the local site	No additional imaging required	Discontinue treatment (exception is possible upon consultation with sponsor)	No additional imaging required	N/A
Repeat tumor imaging shows iSD, iPR or iCR by the local site	Continue regularly scheduled imaging assessments	Continue study treatment at the local site Investigator's discretion	Continue regularly scheduled imaging assessments	May restart study treatment if condition has improved and/or clinically stable per Investigator's discretion.

iCR = complete response per irRECIST; iPD = progressive disease per irRECIST; iPR = partial response per irRECIST; irRECIST = immune-related Response evaluation Criteria in Solid Tumors; PD = progressive disease

*Note: Clinically unstable patients are not required to undergo confirmation of PD. This decision is left to the discretion of the investigator.

Confirmation of Disease Progression:

In subjects who have initial evidence of radiological iPD, it is at the discretion of the PI whether to continue a subject on study treatment until repeat imaging is obtained based on their assessment of clinical stability. Subjects may receive study treatment and tumor assessment should be repeated ≥ 4 weeks later in order to confirm iPD by per site assessment.

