Clinical stability is defined as the following:

- 1) absence of symptoms and signs indicating clinically significant progression of disease, including worsening of laboratory values
- 2) no decline in ECOG performance status

- 3) absence of rapid progression of disease
- 4) absence of progressive tumor at critical anatomical sites (eg, compression) requiring urgent alternative medical intervention

In determining whether or not the tumor burden has increased or decreased per irRECIST, the local site investigator should consider all target and non-target lesions as well as any incremental new lesion(s).

iPD is confirmed at repeat imaging if ANY of the following occur by irRECIST:

- Tumor burden remains $\geq 20\%$ and at least 5 mm absolute increase compared to nadir
- Non-target disease resulting in initial PD is worse (qualitative assessment)
- New lesion resulting in initial PD is worse (qualitative assessment)
- Additional new lesion(s) since last evaluation
- Additional new non-target progression since last evaluation (i.e non-target progression following initial iPD in which iPD was due to either increased target lesion tumor burden or a new lesion but was not confirmed on repeat imaging).

Note: Rapid clinical deterioration does not require confirmation of iPD

If repeat imaging confirms iPD due to any of the scenarios listed above, subjects will be discontinued from study therapy.

NOTE: If a subject has confirmed radiographic progression (ie, 2 scans at least 4 weeks apart demonstrating progressive disease) per irRECIST, but the subject is achieving a clinically meaningful benefit, and there is no further increase in the tumor burden at the confirmatory tumor imaging, an exception to continue treatment may be considered following consultation with the sponsor.

iPD is not confirmed at repeat imaging if ALL of the following occur by irRECIST:

- Tumor burden is $< 20\%$ or < 5 mm absolute increase compared to nadir
- Non-target disease resulting in initial iPD is stable or improved (qualitative assessment)
- New lesion resulting in initial iPD is stable or improved (qualitative assessment)
- No incremental new lesion(s) since last evaluation
- No incremental new non-target progression since last evaluation

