If repeat imaging does not confirm iPD by irRECIST and the subject continues to be clinically stable, treatment may continue and follow the regular imaging schedule. If iPD is confirmed by a consecutive assessment, the first date of iPD documented should be the date of iPD. However, if iPD is not confirmed by a consecutive assessment but is

again noted at a subsequent assessment, the date of iPD documented should be the second date of iPD to capture incremental benefit.

When feasible, subjects should not be discontinued until progression is confirmed by the local site investigator/radiographic assessment. This allowance to continue treatment despite initial radiologic PD takes into account the observation that some subjects can have a transient tumor flare in the first few months after the start of immunotherapy, and then experience subsequent disease response. New lesions will be documented on the CRF form.

Confirmation of Response (iCR or iPR):

To be assigned a status of iCR or iPR changes in tumor measurements must be confirmed by consecutive repeat assessments performed no less than 4 weeks (28 days) after the criteria for response are first met.

The confirmatory assessments for complete response (CR)/partial response (PR) should be completed as close to the 28 day period without waiting for the next scheduled assessment (ie, 9 weeks later in case of subjects on treatment and 12 weeks later for subjects in long term follow-up (LTFU) who have ended treatment for reasons other than PD.

In some circumstances it may be difficult to distinguish residual disease from normal tissue. When the evaluation of iCR depends on this determination, it is recommended that the residual lesion be investigated (ie, biopsy) to confirm the iCR status.

Subjects who have had Complete or Partial Removal/Reduction of the Lesion will be Evaluated as Follows:

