When a target lesion splits into 2 or more lesions, the largest measurable part of the split lesion should be considered to be the previously recorded target lesion with measurements provided for the current assessment and followed for future assessments. The dimensions of the split parts would still be target lesions. When a non-target lesion splits into 2 or more lesions, the split parts remain non-target lesions for the duration of the study. Any new lesions that result from separating should be documented as lesions that were generated by separating and not truly new lesions.

Table 14. Matrix for Determining the Overall Response at Each Assessment Point for irRECIST

Target Lesions (tumor burden) ^a	Non-target Lesions	New Lesions	Visit Overall Response	Subject Overall Response
↓ 100%	Absent / NA	Absent	iCR	iCR ^b
	Stable	Absent	iPR	iPR ^b
	Qualitatively worse	Absent	iPD	iPR if no further worsening of non-target lesions ^{b,c}
↓ ≥ 30%	Absent / Stable / NA	Present	iPD	iPR if stable new lesions and no additional new lesions ^{b,c}
	Absent / Stable / NA	Absent	iPR	iPR ^b
	Qualitatively worse	Absent	iPD	iPR if no further worsening of non-target lesions ^{bc}
↓ < 30% to ↑ < 20%	Absent / Stable / NA	Present	iPD	iPR if new lesions stable and no additional new lesions ^{b,c}
	Absent / Stable / NA	Absent	iSD	iSD if ≥ 8 weeks from start of study therapy; otherwise, UE
	Qualitatively worse	Absent	iPD	iSD if no further worsening of non-target lesions ^c
↑ ≥ 20% and ↑ ≥ 5 mm absolute UE	Absent / Stable / NA	Present	iPD	iSD if stable new lesions and no additional new lesions ^c
	Any	Any	iPD	iPD ^c
	Absent / Stable / NA	Absent	iUE	iUE
iCR/iPR/iSD	Qualitatively worse	Absent	iPD	iPD ^c
	Absent / Stable / NA	Present	iPD	iPD ^c
	ND/iUE	Absent	iUE	iUE
	ND/iUE	Present	iPD	iPD

iCR = complete response (per irRECIST); NA = not applicable; ND = not done; iPD = progressive disease (per irRECIST); iPR = partial response (per irRECIST); iSD = stable disease (per irRECIST); iUE = unable to evaluate (per irRECIST)

^a Decrease relative to baseline; increase relative to nadir.

^b Confirmation or iCR/iPR required by a repeat consecutive assessment no less than 4 weeks (28 days) from the date first documented. For iCR, any pathological lymph nodes (whether target or non-target) must have reduction in short axis to < 10 mm. The subject overall response will be iSD if iCR/iPR is not confirmed.

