^c In the absence of clinical instability, an initial visit overall response of iPD must be consecutively confirmed no less than 4 weeks (28 days) from the date first documented for a subject overall response of iPD. The onset of iPD will be at the initial visit overall response of iPD when it is confirmed. If the initial visit overall response of iPD is not confirmed, then a subsequent iPD does not need to be confirmed for a subject overall response of iPD.

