* , iPD, iPD, * * , iPDrcd, * * , iPD, non-iPD, iPD, * iPDrcd = iPD from rapid clinical deterioration as the reason for ending radiographic follow-up.	iPD, iPD iPD, iSD, iPD, iPD iPD, iUE, iPD iPDrcd	iPD	Criteria for iBOR=iCR, iPR, or iSD not met. A consecutive confirmatory iPD must be no less than 4 weeks (28 days) later unless there is rapid clinical deterioration; iPDrcd does not require confirmation. If an initial visit overall response of iPD is not confirmed, then a subsequent iPD does not need to be confirmed for a subject overall response of iPD.
* , iSD, * iPD	iSD iUE, iSD iPD iUE, iPD	iUE	Criteria for iBOR=iCR, iPR, iSD, or iPD not met. iSD must be < 56 days from first dose (phase 1b).

Best overall response (BOR) per RECIST v1.1

Best overall response (BOR) of complete response (CR), partial response (PR), stable disease (SD), progressive disease (PD) or unevaluable (UE) will be derived based on investigator assessment using RECIST v1.1 (see protocol Appendix E). The visit overall response assessments occurring after initiation of non-study anticancer therapy **will not be included. The visit overall response assessments occurring on or after a complete or partial removal/reduction of any target or non-target lesion containing cancer or with unknown pathology results will not be included except a PD observation.**

Confirmation of CR and PR is not required. For the derivation of BOR, the overall visit response will be UE if SD is earlier than 56 days **after the date of first dose**. As indicated in protocol Table 15, BOR is defined as the best overall visit response in the following order: CR, PR, PD, SD, or UE.

BOR per modified RECIST v1.1 for Phase 1b subjects will follow the same derivation.

Disease control rate (iDCR) per irRECIST

Disease control rate (iDCR) per irRECIST is defined as the incidence of an iBOR of iCR or iPR or iSD among the set of subjects analyzed.

Disease control rate (DCR) per RECIST v1.1

Disease control rate (DCR) per RECIST v1.1 is defined as the incidence of a BOR of CR or PR or SD among the set of subjects analyzed.

Duration of response (iDOR) per irRECIST

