Objective response rate (ORR) per RECIST v1.1

ORR is defined as the incidence of a BOR of CR or PR per RECIST v1.1 among a set of subjects analyzed. Subjects with a CR or PR will be defined as responders. Subjects who do not have any follow-up tumor assessments will be regarded as non-responders per RECIST v1.1.

Overall Survival (OS)

OS is defined as the interval from first dose (phase 1b) to the event of death from any cause; otherwise, OS is censored at the date the subject was last known to be alive. Subjects with a vital status (alive or dead) obtained after the data cut off will be censored at the date cutoff date.

Pembrolizumab Adverse Events of Special Interest (AEOSI)

AEOSI for pembrolizumab are immune-mediated events and infusion-related reactions, which represent the known risks for and are considered causally associated with, pembrolizumab. A pre-specified list of preferred terms (PTs) based on MedDRA was developed by Merck to consistently characterize the nature and frequency of each AEOSI across the clinical program, regardless of causality as reported by investigators. These PTs are considered to be medically equivalent to the identified risks for pembrolizumab.

Pembrolizumab Event of Clinical Interest (ECI)

Pembrolizumab Events of Clinical Interest include: an overdose of pembrolizumab as defined in protocol Section 9.6, and potential drug-induced liver injury (DILI) from pembrolizumab as defined in protocol Section 9.7.

Potential Follow-Up Time

Potential follow-up time for a subject is calculated from the enrollment (phase 1b) date to the analysis data cutoff date.

Progression-free survival (iPFS) per irRECIST

Progression-free survival (iPFS) per irRECIST is defined as the interval from first dose (phase 1b) to the earlier of a subject overall response of iPD (see protocol Table 14) or death from any cause; otherwise, iPFS is censored at the last evaluable tumor assessment. The initial date of an iPD that is consecutively confirmed will be the iPFS date.

Progression-free survival (PFS) per RECIST v1.1

Progression-free survival (PFS) per RECIST v1.1 is defined as the interval from first dose (phase 1b) to the earlier of a subject overall response of PD (see protocol Table 16) or death from any cause; otherwise, PFS is censored at the last evaluable tumor assessment.

Safety Follow-up Visit

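### Table 14, its footnote c and SAP Table 1 give conflicting iPD outcomes for a new lesion that appears and then stays stable, and for a clinically unstable subject who later responds

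*Protocol*

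**What the plan says.** Protocol Appendix D:

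- **Table 14, visit column.** The visit overall response is iPD whenever a new lesion is present. Stability is not considered.
- **Table 14, subject overall column.** With target lesions in the response range and a new lesion present, the entry is "iPR if stable new lesions and no additional new lesions". The stable-disease range has the matching iSD entry. Two other new-lesion rows (target lesions unevaluable; non-target lesions not done or unevaluable) give iPD with no stability condition.
- **Confirmation of Disease Progression.** Repeat imaging does not confirm iPD when the lesion that triggered it is stable or improved and the other listed conditions are met. If iPD is noted again later, "the date of iPD documented should be the second date of iPD to capture incremental benefit".
- **Table 14, footnote c.** "In the absence of clinical instability, an initial visit overall response of iPD must be consecutively confirmed" at least 28 days later to become a subject overall iPD. The footnote ends: "If the initial visit overall response of iPD is not confirmed, then a subsequent iPD does not need to be confirmed".
- **Table 13.** A clinically unstable subject may be rescanned. If the scan shows iSD, iPR or iCR, the table reads "May restart study treatment if condition has improved and/or clinically stable", so later evaluable scans are foreseen.

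SAP Section 6:

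- iPFS is "the interval from first dose (phase 1b) to the earlier of a subject overall response of iPD" or death, with a pointer to protocol Table 14. iDOR ends on the same subject overall response.
- Table 1 derives iBOR from the sequence of visit responses. Two consecutive iPDs at least 28 days apart are confirmed iPD. It repeats the waiver: "If an initial visit overall response of iPD is not confirmed, then a subsequent iPD does not need to be confirmed". It also waives confirmation for iPDrcd, defined as rapid clinical deterioration that was the reason radiographic follow-up ended.

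**The concern.** A new lesion that appears and then stays unchanged is one of the patterns irRECIST was adopted to accommodate. For that pattern the documents contain several rules that disagree, and none is given precedence. The term subsequent iPD is not defined. It could mean any later visit coded iPD, including one coded iPD only because the same stable lesion is still there, or it could mean fresh worsening.

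Two programmers could each follow the text and report different iPFS and iDOR for the same subject. The instability exception raises a second problem: one subject could be a confirmed responder in iBOR and have an iPFS event dated before the response began.

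**Working it through.** The plan states no figure on this point, so there is none to reproduce. The check applies each stated rule to the same scan sequences.

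**Inputs.** Scans are at weeks 9 and 18 and then every 9 weeks (Protocol 3.1.3.2). A repeat scan at week 13 is assumed, the earliest allowed by the 4-week rule.

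**Sequence 1: new lesion first seen at week 9, unchanged afterwards; target lesions in the stable range; nothing else worsens.**

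| | Week 9 | Week 13 | Week 18 | Week 27 |
|---|---|---|---|---|
| Visit column | iPD | iPD | iPD | iPD |
| Subject overall column | awaiting confirmation | iSD | iSD | iSD |

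With target lesions in the response range, iSD becomes iPR.

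1. *The stability condition in the subject overall column governs.* There is no event, and iPFS is censored at the last evaluable scan.
2. *Footnote c is applied to the visit column.* Week 13 does not confirm, because the lesion is stable. Week 18 is again a visit iPD and needs no confirmation. The event is at week 18, without growth.
3. *The SAP Table 1 pattern of two consecutive iPDs is applied to the visit column.* Weeks 9 and 13 are 4 × 7 = 28 days apart, so iPD counts as confirmed. The SAP dates a confirmed iPD at its first occurrence, week 9.

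Readings 2 and 3 differ by 18 − 9 = 9 weeks. Reading 1 has no event through week 27, which is 27 − 18 = 9 weeks past reading 2 and 27 − 9 = 18 weeks past reading 3.

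**Effect on iBOR.** With target lesions in the response range, the subject overall column gives iPR at weeks 13 and 18. These are 5 × 7 = 35 days apart, which meets the 28-day rule, so iBOR is iPR. With target lesions in the stable range, iSD at week 13 falls about 13 × 7 = 91 days after first dose, past the 56-day minimum, so iBOR is iSD. If the visit column is fed into SAP Table 1 instead, every entry is iPD and iBOR is iPD in both cases. iORR and iDCR are defined from iBOR and would follow it.

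**Sequence 2: as sequence 1, but at week 18 the target lesions are unevaluable or the non-target lesions are not done.** The applicable Table 14 row gives subject overall iPD at week 18 even under reading 1. At week 27 the same unchanged lesion would again be coded iSD.

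**Sequence 3 (control): new lesion gone at week 13; target burden then up by at least 20% and 5 mm at week 18.** All readings give an event at week 18, so the rules agree when there is real growth.

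**Sequence 4: iPD at week 9 in a clinically unstable subject, then iPR at weeks 13 and 18.** Footnote c asks for confirmation only in the absence of instability, so week 9 is a subject overall iPD and an iPFS event. In SAP Table 1 the week 9 finding is not iPDrcd, because radiographic follow-up continued. The two iPRs are 35 days apart, so iBOR is a confirmed iPR. The iPFS event is dated 13 − 9 = 4 weeks before the first response, and iDOR has to disregard the iPD that ended iPFS.

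**The case against.** The strongest defence is that iPFS and iDOR are triggered by the subject overall response, and for the main rows that column keeps a stable new lesion at iSD or iPR. Footnote c waives confirmation; it does not say that the stability condition lapses. SAP Table 1 shows a pattern of iPD, then a visit that is not iPD, then iPD, which looks like recurrence after a refuting scan. The week-18 result also mixes tests, using lesion stability at week 13 and the visit column at week 18. For unstable subjects, iPDrcd by definition excludes anyone who goes on being scanned.

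Much of this stands. Reading 1 is available in the main rows and may well be what was intended. But it is nowhere stated. Footnote c sits on the very cells that carry the stability condition and begins from the visit response. A persistently present lesion never produces a visit that is not iPD, so the Table 1 recurrence pattern cannot arise from the visit column. The unevaluable and not-done rows fail even under reading 1. The iPFS definition points to Table 14 and not to iPDrcd.

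A reader might go further and infer that the refuted first iPD itself becomes final, or that the rule cancels the pseudoprogression allowance and biases iPFS and iDOR downward overall. The documents do not support that. Appendix D sets aside an unconfirmed first iPD and uses the later date, a reading with no event exists in the main rows, and no rate of persistent stable new lesions is given.

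**Conclusion.** The conflict is real and should be resolved, but its reach is limited. For a persistent stable new lesion the text supports no event, an event at week 18 or an event at week 9. In two Table 14 rows it gives iPD without growth regardless of stability. For an unstable subject who later responds, iPFS and iBOR can contradict each other.

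The overall size cannot be derived. The Efficacy Analysis Set is expected to hold about 27 subjects, so one subject is 1/27 = 3.7% of it, but the documents do not say how many subjects would be affected. A reader might turn this into a shift in a 6-month iPFS rate. That would need an assumed count, and the SAP defines landmark rates only for OS.

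The affected results are descriptive phase 1b iPFS and iDOR, and iBOR if visit responses go straight into SAP Table 1. The DLT primary endpoint is untouched, and SAP Section 11 states that no phase 3 analyses will be performed. The conclusion assumes the week-13 repeat scan. Row alignment in Table 14 should be checked against the typeset page; the stability wording belongs to new-lesion cells either way.

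**What to change.** For endpoint derivation only; treatment decisions are not addressed here.

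1. In footnote c and in SAP Section 6 and Table 1, define a subsequent iPD after a non-confirmed iPD as one that meets an item on the existing Appendix D list for confirming iPD, with new evidence since the non-confirming scan.
2. State that a persistent stable new or non-target lesion alone takes the iPR or iSD of the subject overall column, and is neither a confirming nor a subsequent iPD.
3. Apply the same stability condition to the rows with target lesions unevaluable or non-target lesions not done or unevaluable: iUE instead of iPD if the new lesion is stable.
4. Align iPFS and iDOR with the SAP iPDrcd rule, so that an unconfirmed iPD under clinical instability counts only if no later evaluable scan refutes it.
5. Record that the change was made after the primary analysis, and show iPFS and iDOR under both derivations for any affected subject.

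The cost is a few sentences in Appendix D and SAP Section 6 and a programming change on data already collected. Appendix D already calls for qualitative evaluation of new lesions at each time point.

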Appendix E. RECIST v1.1 Guidelines for Assessment of Disease Response

(Phase III Only)

For phase III only, investigators will be asked to obtain and document tumor responses per standard RECIST v1.1 along with those per irRECIST at every scheduled and unscheduled tumor assessment following the same target and non-target lesions determined for irRECIST tumor response assessment. Clinical decisions for treatment, however, should only be made based on tumor assessment using irRECIST.

Method of Measurement of Tumor Lesions:

Note: Imaging scans obtained for irRECIST tumor response assessment should also be used for RECIST v1.1 assessment

CT scans (or MRI):

Computed tomography (CT) scans by contrast-enhanced or spiral scan (or magnetic resonance imaging [MRI] scan) will be performed to evaluate tumor response for visceral or nodal/soft tissue disease (including lymph nodes). The same method of assessment and the same technique should be used to characterize each identified and reported lesion at baseline and during follow-up. A switch from contrast enhanced CT to noncontrast CT or to MRI (or vice versa) should not preclude response assessment if, in the judgment of the site radiologist, there is no significant difference in the assessment by changing modalities. This may occur if a subject has developed a medical contraindication to intravenous contrast for CT scans while on trial. This change would require the preapproval of the sponsor medical monitor.

Positron Emission Tomography (PET)/CT Scans:

If a combined PET/CT scan is performed at the discretion of the investigator, the CT portion of that exam should not be substituted for the dedicated CT exams required by this protocol. The PET portion of the CT may introduce additional data which may bias the investigator assessment of response if it is not routinely or serially performed. However, if the investigator or the site radiologist can document that the CT performed as part of a PET/CT is of identical diagnostic quality to a diagnostic CT (with intravenous and oral contrast) then the CT portion of the PET/CT can be used for tumor measurements.

Ultrasound:

Ultrasound (US) should not be used as a primary method to assess lesion measurements in response to treatment.

Note: Tumor Lesions designated for irRECIST response assessment should also be used for RECIST v1.1.

Baseline Lesions

Measurable Lesions:

Measurable lesions are defined at baseline as lesions that can be accurately measured in at least one dimension (ie, longest diameter for non-nodal lesions and short axis for lymph nodes will be measured and followed) with a minimum size of:

- ≥ 10 mm by CT scan (CT scan slice thickness no greater than 5 mm) or MRI
A lymph node must be ≥ 15 mm in short axis when assessed by CT scan or MRI.

Non-Measurable Lesions:

All other lesions, including small lesions (longest diameter < 10 mm or pathological lymph nodes with ≥ 10 mm but < 15 mm short axis) and other truly non-measurable lesions are considered non-measurable. Examples of non-measurable lesions include some bone lesions, ascites, pleural/pericardial effusion, lymphangitic involvement of the skin or (lymphangitis cutis/pulmonis), cystic lesions, and groups of lesions that are small and numerous.

Documentation of "Target", "Non-Target" and "New" Lesions:

Baseline evaluations will be used to prospectively identify all sites of disease present as close as possible to the enrollment and never greater than or equal to 28 days before the enrollment date. Sites of disease will be characterized as either target, non-target lesions or new lesions.

Baseline Documentation of Target Lesions:

Up to 5 target lesions (a maximum of 2 per organ) will be chosen to measure over the course of therapy (Phase III). Pathological lymph nodes that are defined as measurable must meet the criterion of a short axis of ≥ 15 mm by CT scan in order to be identified as target lesions.

Target lesions should be selected on the basis of their size (lesions with longest diameter) and suitability for accurate repeated measurements by radiographic imaging.

In situations where larger lesions cannot be accurately measured repeatedly (eg, near the diaphragm where respiratory changes may affect measurements), smaller lesions that meet criteria for measurability may be selected instead. Target lesions must not be chosen from a previously irradiated field unless there has been documented tumor progression in that field prior to enrollment. The distribution of the target lesions should be representative of the subject's overall disease (eg, largest lesions per organ).

A sum of the diameters (longest for non-nodal lesions, short axis for nodal lesions) for all target lesions will be calculated and reported as the baseline sum diameters. The baseline sum of diameters will be used as reference by which to characterize the objective tumor response.

Baseline Documentation of Non-Target Lesions:

Any measurable lesions that were not chosen as target lesions and pathological lymph nodes with short axis ≥ 10 mm but < 15 mm, as well as non-measurable lesions should be identified as non-target lesions. Non-target lesions are evaluated at each timepoint but measurements are not required.

Documentation of New Lesions:

Any new lesion that appears during the course of study will be categorized as a new lesion. New lesions are evaluated at each timepoint but measurements are not required.

Tumor Assessment per RECIST v1.1:

At each subsequent tumor assessment after baseline, the sum of diameters of target lesions (longest for non-nodal lesions and short axis for nodal) will contribute to the total tumor burden.

$$\text{Tumor Burden} = \text{sum of diameter of target lesions}$$

New lesions and non-target lesion measurements are not required and these lesions should be followed qualitatively.

Response Evaluation:

Evaluation of Objective Response:

The subject response will be assessed based on tumor burden (the sum of diameters of target lesions) and qualitative assessment of non-target lesions per the definitions in [Table 15](#).

Table 15. Definition of Tumor Response for RECIST v1.1

Evaluation of Target Lesions	
Complete Response (CR)	Disappearance of all non-nodal target lesions. Any pathological lymph nodes (whether target or non-target) must have reduction in short axis to <10 mm.
Partial Response (PR)	At least a 30% decrease in the sum of diameters of target lesions, taking as reference the baseline sum diameters.
Progressive Disease (PD)	At least a 20% increase in the sum of diameters of target lesions, taking as reference the smallest sum on study (this includes the baseline sum if that is the smallest on study). In addition to the relative increase of 20%, the sum must also demonstrate an absolute increase of at least 5 mm. (Note: the appearance of one or more new lesions is also considered progression)
Stable Disease (SD)	Neither sufficient shrinkage to qualify for PR nor sufficient increase to qualify for PD, taking as reference the smallest sum diameters while on study
Unable to Evaluate (UE)	Any non-target lesion present at baseline which was not assessed or was unable to be evaluated leading to an inability to determine the status of that particular tumor for that time point
Not Done (ND)	Scans were not performed at this time point to evaluate target lesions
Evaluation of Non-target Lesions	
Complete Response (CR)	Disappearance of all non-target lesions and normalisation of tumour marker level. All lymph nodes must be non-pathological in size (<10mm short axis)
Non-CR/Non-PD	Persistence of one or more non-target lesion(s).
Progressive Disease (PD)	Unequivocal progression of existing non-target lesions. (Note: the appearance of one or more new lesions is also considered progression).
Unable to Evaluate (UE)	Any non-target lesion present at baseline which was not assessed or was unable to be evaluated leading to an inability to determine the status of that particular tumor for that time point
Not Done (ND)	Scans were not performed at this time point to evaluate target lesions

RECIST = Response Evaluation Criteria in Solid Tumors

Target Lesions:

- All target lesions (nodal or non-nodal) should have the actual measurements recorded at each subsequent evaluation even when very small (eg, 2 mm) if possible.
- Any non-nodal target lesion that become ‘too small to measure’ a default value of 5 mm should be assigned. If the lesion has disappeared, 0 mm should be recorded.
- Any nodal target lesion that become ‘too small to measure’ a default value of 5 mm should be assigned for its short axis.

- Coalescing lesions: If a plane is maintained in aiding the demarcation of the 2 lesions, then the maximal diameter of each individual lesion should be recorded. If the lesions have truly coalesced, then the longest diameter should be used for the coalesced lesion and assigned to the largest of the coalesced lesions. The smaller of the lesions then should be recorded as 0 mm. If target lesion(s) coalesces with non-target lesion(s), the longest diameter should be used for the coalesced lesions and assigned to the largest of the coalesced target lesion(s). If a target lesion merges with a non-target lesion, the non-target lesion should be absent from the current visit and all future assessments, and the target lesion should include both merged lesions for recording measurements. New lesions and enlarging non-target lesions are measured qualitatively.
- Splitting lesions: When a target lesion splits into 2 or more lesions, the largest measurable part of the split lesion should be considered to be the previously recorded target lesion with measurements provided for the current assessment and followed for future assessments. The dimensions of the split parts would still be target lesions. Any new lesions that result from separating should be documented as lesions that were generated by separating and not truly “new” lesions.

Non-Target Lesions

- Coalescing lesions: When 2 or more non-target lesions merge, the smaller lesion should be recorded as absent for the current and all future assessments, and the larger lesion should be recorded as present for the current assessment and followed for future assessments.
- Splitting lesions: When a non-target lesion splits into 2 or more lesions, the split parts remain non-target lesions for the duration of the study. Any new lesions that result from separating should be documented as lesions that were generated by separating and not truly new lesions.
- In contrast to irRECIST, to achieve progression of disease of non-target lesions, ‘unequivocal progression’ of these lesions must be documented on the basis that there must be an overall level of substantial worsening in non-target disease such that, even in presence of SD or PR in target disease, the overall tumor burden has increased sufficiently to merit discontinuation of therapy. A modest increase in the size or “qualitative worsening” as described for irRECIST assessment would not suffice to achieve ‘unequivocal progression’ status per RECIST v1.1.

New Lesions

- A new lesion should be unequivocal. If a new lesion is equivocal, continued therapy and follow-up evaluation should ensue until it is clear that it represents a new lesion, then progression should be declared using the date of the initial scan.
- Appearance of new malignant lesions on a follow up study in an anatomical location that was not scanned at baseline is considered a new lesion and will indicate disease progression.

Subjects who have had Complete or Partial Removal/Reduction of the Lesion will be Evaluated as Follows:

- The procedure itself and all post-procedure lesion assessments should always be recorded in the CRF. A completely resected lesion should be assigned a default code of 0 mm (for target lesions) or “absent” (for non-target lesions). A partially resected lesion should be assigned its measurement post-procedure (for target lesions) or “present” (for non-target lesions). If the resected lesion contains no cancer under pathology evaluation, subsequent tumor assessments post-procedure may be used for tumor burden calculations and/or determination of response. If the resected lesion contains cancer or pathology results are unknown, the recorded tumor assessments post-procedure may be used for tumor burden calculations, but determination of response will be considered unable to evaluate (UE) for response except in the case of PD. If the new tumor burden post-procedure is lower than the nadir before the procedure, then the new nadir will be set to the post procedure tumor burden. Otherwise, the previous pre-procedure nadir will be retained as the nadir. Subsequent assessments for PD will be determined from the nadir.

Evaluation of visit overall response

A summary of the overall response determination at each evaluation time point is provided in [Table 16](#).

Table 16. Matrix for Determining the Overall Response at Each Assessment Point for RECIST v1.1

Target Lesions	Non-target Lesions	New Lesions	Visit overall response
CR	CR	No	CR
CR	Non-CR/non-PD	No	PR
CR	UE/ND	No	PR
CR	NA	No	CR
PR	Non-PD/NA/UE/ND	No	PR
SD	Non-PD/NA/UE/ND	No	SD
PD	Any	Yes or No	PD
Any	PD	Yes or No	PD
Any	Any	Yes	PD
UE	Non-PD/NA	No	UE
ND	Non-PD/NA	No	UE

CR = complete response; NA = no non-target lesions at baseline; PD = progressive disease; PR = partial response; SD = stable disease

Non-/CR/Non-PD : Persistence of one or more non-target lesion(s) and/or maintenance of tumor marker level above the normal limits; UE = unevaluable

